- Overall survival (OS) will be the primary endpoint of this study, survival time will be defined as the duration from the date of randomization until death. Subjects who are alive at the data inclusion cutoff date for the analysis will be censored at that date and survival time will be defined as time from randomization to censor date. Patients lost to follow-up and untraceable for survival status will be censored on the last date subject was known to be alive or lost to follow-up. The overall survival between the Xilonix™ + BSC group and placebo + BSC group will be compared using an unadjusted log-rank test.

3.2 Secondary Efficacy Endpoints:

Secondary efficacy variables will include 1) change in lean body mass (LBM) measured by dual-energy X-ray absorptiometry (DEXA) scans, 2) change in function, symptoms and overall quality of life assessed through the cancer-specific EORTC QLQ-C30¹ questionnaire, 3) change of platelet counts, 4) progression free survival (PFS), 5) objective response rate (ORR) 6) disease control rate (DCR)

The change from baseline on LBM, EORTC score, and platelet count will be calculated by subtracting the baseline (screening) value from that at follow-up (cycle 5 day 1 or off-study visit for patients who completed at least cycle 3 day 1).

Quality of life (QoL) in patients participating in the trial will be evaluated using the European Organization for Research and Treatment of Cancer (EORTC) version 3.0 questionnaire (Appendix). The EORTC QLQ-C30 questionnaire incorporates nine multi-item scales: five functional scales (Physical, Role, Cognitive, Emotional and Social); three symptom scales (Fatigue, Pain and Appetite loss); and a Global Health Status/QoL scale. Each item, excepting Global Health Status, is answered on a four-point scale: “not at all”, “a little”, “quite a bit”, and “very much”. Response to Global Health Status is measured on a 1 to 7 scale, 1 being “very poor” and 7 being “excellent”. Using EORTC specified methodology (Appendix); responses to all the scales will be linearly transformed to reach the scale range 0 to 100.

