Objective Response Rate (ORR): The ORR will be estimated by dividing the total number of patients with confirmed complete response (CR) and partial response (PR) by the total number of patients in the ITT population.

Disease Control Rate (DCR): The DCR will be estimated by dividing the total number of patients with confirmed CRs, PRs and stable disease (SD) by the total number of patients in the ITT population.

3.3 Exploratory Endpoint:

Clinical Response Rate (CRR) will be the exploratory endpoint for this study. This will be a composite measure assessing the change in LBM, fatigue, pain, and appetite from baseline to week 8. Clinical response will be defined as, 1) Improvement or stabilization (≥ 0 kg change) of LBM as assessed by DEXA scan, and 2) Improvement or no worsening (≤ 0 score point change; low scores reflect better functioning and lower symptom distress) on any two of the three symptom scale measures (fatigue, pain, appetite) of EORTC QLQ-C30. Patients missing the follow-up assessment will be considered non-responders.

3.4 Safety Endpoints:

Safety endpoints will be evaluated by monitoring adverse events from clinical and laboratory reporting. Adverse events will be graded according to the National Cancer Institute Common Terminology Criteria for Adverse Events (NCI-CTCAE, version 4.0). Significant trends in the distribution and severity of the adverse events across the study groups will be assessed.

4 Independent Data Monitoring Committee (IDMC):

An Independent Data Monitoring Committee (IDMC) will be formed to safeguard the interests of trial participants, assess the safety and efficacy of the interventions during the trial, and monitor the overall conduct of the clinical trial. The committee will meet after every 200 subjects enrolled (or 6 months, whichever occurs first) until the first interim analysis to monitor early evidence of treatment harm, and make any appropriate recommendations. After the first interim analysis, the meeting will occur at each subsequent analysis or every year, whichever occurs first. IDMC recommendations will include whether to continue, suspend, or otherwise modify enrolment. Monitoring for early toxicity will be continuous until the first interim analysis, after which this monitoring will occur at each subsequent scheduled interim analysis or every year, whichever occurs first. Full details of the role and responsibilities of the IDMC are described in the IDMC charter.

5 Sample Size and Power

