Another supportive analysis will include a multivariate Cox proportional hazards regression (CPH) method assessing independent predictors of OS after adjusting for potential confounders. Selection of covariates will primarily be based on *a priori* knowledge, and include age (continuous scale), prior cancer therapy (number of regimens will be entered on continuous scale), ECOG performance status (2 categories ECOG 0 and 1 pooled together, and ECOG 2), and KRAS mutation status (coded as no=0, yes=1), and baseline body mass index (BMI). Covariates may be excluded from model if the number of patients representing 1 level of that variable is insufficient. A backward selection method will be used for variable selection; the p-value threshold will be set at 0.10. The proportional-hazard assumption will be tested by Schoenfeld residual analysis. The hazard ratio (HR) and 95% Wald confidence interval (CI) for the HR will be computed and presented in the results. The CPH analysis will be exploratory in nature.

8.4.2 Secondary Effectiveness Endpoints:

LBM: LBM change will be compared across treatment groups both by responder analysis and assessing absolute change.

Patients showing stabilization or improvement from baseline (≥ 0 kg change) will be considered LBM responders and those experiencing LBM reduction will be defined as non-responders. Patients not having a second evaluation for going off the study or any other reason will be considered non-responders. LBM response rate will be compared using Pearson chi-square test. Proportion by group, relative risk and odds ratio estimates will be presented with Cochran-Mantel-Haenszel (CMH) 95% confidence intervals (95% CI).

Absolute change will be compared between treatment groups using an analysis of covariance (ANCOVA) method (SAS GLM procedure) with treatment groups as the factor and baseline value as covariate. The difference in least-square means and 2-sided P values will be derived from the ANCOVA model.

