EORTC: Longitudinal and descriptive analysis will be performed to assess patient reported outcomes (PRO). The EORTC survey results will be converted to domain specific scores using the prescribed algorithm (Appendix A). Scores on the EORTC QLQ-C30 functional and symptom scales will be summarized according to the randomization groups. The EORTC survey responses will be converted to domain specific scores using the prescribed algorithm. Scores on EORTC QLQ-C30 functional and symptom scales will be summarized according to the randomization groups. Descriptive statistics of PRO score will be summarized by treatment group.

Patients showing stabilization or improvement from baseline (≤ 0 change) on any two of the three symptom scales (pain, fatigue, appetite loss) will be considered EORTC responders. Patients experiencing reduction or worsening on the symptom scales will be defined as non-responders. Patients missing the follow-up assessment will be considered non-responders. The comparison of responder rate and absolute change will be performed similar to as described for LBM.

Clinical Response Rate: Patients responding on LBM (≥ 0 kg change from baseline) and EORTC (≤ 0 change on any two three symptoms) will be considered Clinical Responders. Patients missing follow-up status will be considered non-responders. Clinical Response Rate will be compared using a Pearson chi-square test. Proportion by treatment groups and relative risk estimates will be presented with CMH 95% confidence intervals.

Platelet Count: Change in platelet count from baseline to follow-up will be compared between treatment groups using the ANCOVA method described above. The last visit cycle where at least 20 patients per group are on study will be used for follow-up data cut-off for this measure. Trend line plots displaying the median platelet count over time (visit cycles) by treatment groups will be generated.

Progression Free Survival (PFS): PFS will be compared by Kaplan-Meier method using log-rank test. Kaplan-Meier plots by treatment arm will be produced, and point estimates and 95% CIs will be summarized.

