Objective Response Rate (ORR): The RR will be estimated by dividing the total number of patients with confirmed complete response (CR) and partial response (PR) by the total number of patients in the ITT population. Best overall response (BOR), determined from the sequence of cycle responses assessed, will be used for analysis purposes. Response rates will be compared between treatment groups using a Pearson Chi-square test and Wald 95% confidence intervals for the response rate in each treatment groups will be calculated.

Disease Control Rate (DCR): The DCR will be estimated by dividing the total number of confirmed CRs, PRs and stable disease (SD) by the total number of patients in the ITT population. DCR will be analyzed as described for ORR. Best overall response (BOR), will be used for DCR analysis. DCR will be analyzed as described for ORR.

Inferential analysis for the secondary endpoints, without multiplicity correction, will be carried out separately for stratification variables (age, prior therapy, ECOG performance status, KRAS mutation status, and prior regorafenib treatment status), One-way ANOVA and Fisher's exact tests will be used to compare differences across stratification groups. Proportions by treatment group along with 95% CI will be reported.

A two-tailed p value of <0.05 will be considered statistically significant for all secondary endpoints. SAS 9.2 or higher (SAS Institute Inc., Cary, NC) will be used for statistical analysis.

8.4.3 Additional Exploratory Analyses:

Additional analyses will be performed comparing the primary overall survival endpoint, the secondary endpoints, and incidence of SAE, between Clinical Responders and Non-responders. The statistical methodology in conducting these analyses will follow the same described in the primary and secondary efficacy analysis and safety analysis sections.

8.4.1 Pharmacodynamics (PK) analysis:

PK samples will be tested by XBiotech laboratory for a randomly selected patient population as defined in the study protocol. Descriptive statistics of PK parameters will be presented in a table format. The summary will include average MABp1 concentration at visit cycles along with the standard deviation and coefficient of variation (CV).

8.4.2 Analysis of Safety Outcomes:

The assessment of the safety profile will be based on adverse events, vital signs, physical examinations, and clinical laboratory measurements. All randomized subjects, will be included in the safety analysis.

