Relative Risk (95% CI)	X.XX (X.XX to X.XX)	

7) Clinical Response Rate by Treatment Groups PP Population:

XBiotech USA, Inc., Protocol 2012-PT023 V3.6

Interim Analysis #X, Data Date: ddmmmyyyy

	Xilonix+BSC	Placebo+BSC
N	XXX	XXX
Clinical Response, n (% , 95% CI)	XX (XX, XX-XX)	XX (XX, XX-XX)
Difference (effect size)	XX%	
P value from Pearson Chi-Square test (one-tailed)	0.01	
Relative Risk (95% CI)	X.XX (X.XX to X.XX)	

8) Objective Response Rate by Treatment Groups ITT Population:

	Xilonix+BSC	Placebo+BSC
N	XXX	XXX
Objective Response, n (% , 95% CI)	XX (XX, XX-XX)	XX (XX, XX-XX)
Difference (effect size)	XX%	
P value from Pearson Chi-Square test (one-tailed)	0.01	
Relative Risk (95% CI)	X.XX (X.XX to X.XX)	

9) Objective Response Rate by Treatment Groups PP Population:

	Xilonix+BSC	Placebo+BSC
N	XXX	XXX
Objective Response, n (% , 95% CI)	XX (XX, XX-XX)	XX (XX, XX-XX)
Difference (effect size)	XX%	
P value from Pearson Chi-Square test (one-tailed)	0.01	
Relative Risk (95% CI)	X.XX (X.XX to X.XX)	

10) Disease Control Rate by Treatment Groups ITT Population:

	Xilonix+BSC	Placebo+BSC
--	-------------	-------------

XBiotech USA, Inc., Protocol 2012-PT023 V3.6

Interim Analysis #X, Data Date: ddmmyyyy

N	XXX	XXX
Disease Control Rate, n (% , 95% CI)	XX (XX, XX-XX)	XX (XX, XX-XX)
Difference (effect size)	XX%	
P value from Pearson Chi-Square test (one-tailed)	0.01	
Relative Risk (95% CI)	X.XX (X.XX to X.XX)	

11) Disease Control Rate by Treatment Groups PP Population:

	Xilonix+BSC	Placebo+BSC
N	XXX	XXX
Disease Control Rate, n (% , 95% CI)	XX (XX, XX-XX)	XX (XX, XX-XX)
Difference (effect size)	XX%	
P value from Pearson Chi-Square test (one-tailed)	0.01	
Relative Risk (95% CI)	X.XX (X.XX to X.XX)	

12) Secondary Endpoints Results: Change from Baseline

	Placebo+BSC (n= xxx)			Xilonix+BSC (n= xxx)			P*
	Baseline Mean (95% CI)	Follow-up Mean (95% CI)	Change LS Mean±SE	Baseline Mean (95% CI)	Follow-up Mean (95% CI)	Change LS Mean±SE	
Platelet, 1000/cu mm	XXX±XXX	XXX±XXX	X.XX±X.XX	XXX±XXX	XXX±XXX	X.XX±X.XX	0.XXX
PRO: Global QOL Score	XXX±XXX	XXX±XXX	X.XX±X.XX	XXX±XXX	XXX±XXX	X.XX±X.XX	0.XXX
PRO Symptom Score: Pain	XXX±XXX	XXX±XXX	X.XX±X.XX	XXX±XXX	XXX±XXX	X.XX±X.XX	0.XXX
PRO Symptom Score: Fatigue	XXX±XXX	XXX±XXX	X.XX±X.XX	XXX±XXX	XXX±XXX	X.XX±X.XX	0.XXX
PRO Symptom Score: Appetite	XXX±XXX	XXX±XXX	X.XX±X.XX	XXX±XXX	XXX±XXX	X.XX±X.XX	0.XXX
Lean Body Mass, kg	XXX±XXX	XXX±XXX	X.XX±X.XX	XXX±XXX	XXX±XXX	X.XX±X.XX	0.XXX

13) All Adverse Events by CTCAE Grade

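### Every secondary endpoint may be called significant at two-sided p<0.05 with no gate on overall survival, no test order and no adjustment, so no secondary claim has a controlled error rate

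*SAP*

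**What the plan says.** The significance rule is the same in SAP 8.4.2 (Secondary Effectiveness Endpoints) and Protocol 10.4: "A two-tailed p value of <0.05 will be considered statistically significant for all secondary endpoints".

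SAP 3.2 numbers six secondary endpoints: lean body mass (LBM), EORTC QLQ-C30, platelets, PFS and, last, "5) objective response rate (ORR) 6) disease control rate (DCR)". The numbering is a list; nothing calls it a testing order.

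Some endpoints are tested more than once. For LBM, "LBM change will be compared across treatment groups both by responder analysis and assessing absolute change". For EORTC, "The comparison of responder rate and absolute change will be performed similar to as described for LBM". How many EORTC scales are to be tested is not fixed. SAP 3.2 says "The EORTC QLQ-C30 questionnaire incorporates nine multi-item scales", while table shell 12, "Secondary Endpoints Results: Change from Baseline", gives a P column for four: global quality of life, pain, fatigue and appetite.

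The group-sequential boundaries in SAP 5.1 and Protocol 10.3 apply to OS alone. The ORR and DCR shells (8 to 11), like the clinical response rate shells (6 and 7), carry a one-tailed P value, against the two-tailed rule.

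**The concern.** The sentence is an affirmative rule for declaring significance, and nothing labels these p-values nominal or descriptive. Read as written, it has two consequences in a pivotal trial.

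- If OS fails, an LBM, quality-of-life or platelet result with p<0.05 still meets the plan's definition of statistically significant.
- If OS succeeds, claims on the secondary endpoints have no family-wise error control.

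This matters more here than usual, because Protocol 8.3 presents LBM gain as a possible surrogate for anti-tumour activity and stresses symptom benefit.

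**Working it through.** **1. Is OS controlled?** The documents give no family-wise figure for the secondary endpoints, so the figure to reproduce is the OS design. Inputs (SAP 5): HR 0.767, 2:1 allocation, one-sided 0.025, 80% power. A fixed design needs (1.960 + 0.842)² / [(2/9)(ln 0.767)²] = 7.85 / 0.01564 ≈ 502 deaths. A three-stage O'Brien-Fleming design with efficacy and binding futility boundaries at 50/75/100% inflates this by 1.107, to about 555, against the stated 552. The same model gives efficacy p cut-offs of 0.0029, 0.0121 and 0.0254 and futility p of 0.249 and 0.080; SAP 5.1 has 0.0029, 0.0121, 0.025 and 0.25, 0.08. The OS design is reproduced, so the gap lies in the secondary family.

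**2. How many tests?**
- 6: one per endpoint listed in SAP 3.2.
- 11: LBM 2, EORTC responder rate 1, EORTC change 4 (shell 12), platelets 1, PFS 1, ORR 1, DCR 1.
- 16: as above, with nine EORTC scales instead of four.

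**3. Error if the drug has no effect.** For k independent tests, the chance of at least one two-sided p<0.05 is 1 − 0.95^k. Counting only results that favour the drug, it is 1 − 0.975^k. For correlated tests I simulated equicorrelated normal statistics (400,000 draws). The correlations are assumed, because the documents give none.

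| Tests | Either direction, r = 0 / 0.3 / 0.5 | Favouring drug, r = 0 / 0.3 / 0.5 |
|---|---|---|
| 6 | 26.5% / 24% / 21% | 14% / 12% / 10% |
| 11 | 43% / 37% / 30% | 24% / 19% / 15% |
| 16 | 56% / 48% / 37% | 33% / 24% / 19% |

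With a grouped structure (correlation 0.4-0.8 within related endpoints, 0-0.3 between groups), the either-direction figures are 31-39% for 11 tests and 36-48% for 16.

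Not counted: per-protocol repeats (SAP 7.1, SAP 9, shells 9 and 11), analyses by stratification variable, and repeated looks, although the secondary shells carry an interim-analysis header.

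**4. What a gate would do.** If secondary claims require OS success, the chance of any false secondary claim when the drug does nothing is at most the OS alpha, 2.5%, provided the futility stops are followed as the boundaries assume. If OS truly improves and no secondary endpoint does, a fixed order or Holm at two-sided 0.05 holds the family at 5% when the secondary endpoints are tested once, at a time that does not depend on OS.

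Here the time does depend on OS, because testing takes place at whichever look OS crosses. I simulated this with the SAP's efficacy and futility limits, taking equal information fractions for both endpoints and the worst-case OS effect. The favourable error for a null secondary endpoint is about 2.6% at correlation 0.3 with OS, 3.0% at 0.7 and 3.4% at 0.9, against 2.5%.

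**The case against.** The best case on the other side is about size and reading, and most of it stands.

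- A reader might take 56% as the plan's error rate. It needs 16 independent tests. The nine in SAP 3.2 describes the questionnaire; SAP 8.4.2 speaks largely of summarising scale scores, and the only shell with EORTC P values has four scales. Independence does not fit either: LBM response is a cut of LBM change, every ORR responder counts towards DCR, and PFS and DCR share progression. So 56% is a ceiling.
- A reader might take the either-direction rate as the chance of a false benefit claim. It also counts results favouring placebo; the favourable-only rate is about half to 60% of it.
- A reader might infer that the sponsor plans secondary claims after a failed OS test. No passage says so. The documents are silent on any link, and the rule as worded permits it.
- A reader might cite "Inferential analysis for the secondary endpoints, without multiplicity correction, will be carried out separately for stratification variables" as an admission. That sentence concerns analyses by stratification variable, not the main treatment comparisons.
- A reader might add the clinical response rate because it is tested in SAP 8.4.2. SAP 3.3 is clear: "Clinical Response Rate (CRR) will be the exploratory endpoint for this study". It is left out of all the counts above.

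None of this supplies a gate, an order or an adjustment.

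**Conclusion.** The point holds on the text of both documents: two-sided p<0.05 is enough for any secondary endpoint, and only OS has error control. Under no drug effect, the chance of at least one p<0.05 in either direction is about 27% for six independent tests (21-24% at correlations of 0.5-0.3), 30-43% for 11 tests, and at most about 56% for 16. For results favouring the drug it is about 10-33%. These figures rest on how many tests are counted and on assumed correlations of 0 to 0.5. Even the lowest favourable figure, 10%, is four times the 2.5% one-sided level used for OS (10 / 2.5 = 4). This should be corrected before unblinding; it does not affect the OS analysis.

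**What to change.** Replace the sentence in SAP 8.4.2 and Protocol 10.4 with a rule along these lines:

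> Secondary endpoints are tested formally only if OS crosses its efficacy boundary. They are then tested in a fixed order (or by Holm) set by the sponsor before unblinding, each with one named two-sided test in the ITT population, at a family-wise level of 0.05. Formal claims stop at the first failure. All other tests, including per-protocol repeats and further EORTC scales, are reported with estimate and 95% CI and labelled nominal.

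Two additions are needed.

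- **Interim success.** If OS crosses at an interim analysis, either use a group-sequential boundary for the secondary endpoints or accept and state the small excess (favourable error about 2.6-3.4% instead of 2.5%).
- **Sidedness.** Change the one-tailed P in shells 6 to 11 to two-tailed.

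The order, and the choice between responder rate and absolute change for LBM and EORTC, belong to the sponsor; the documents give no basis for preferring one.

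The cost is wording in two documents and some shell edits, with no change to sample size, visits or OS alpha. The downside is real: endpoints after the first failure, or after a failed OS test, cannot be called significant.

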^g DEXA scans will be performed at screening and at Cycle 5 Day 1 (+/- 3 days) to assess changes in body composition. To qualify for inclusion, a site's DEXA should include the following compartments: **bone, fat, and lean**. Results are reported in grams, and should be reported for each extremity, trunk, head, and total, to allow for determination of an axial skeletal muscle index. Patients should be scanned with the **same DEXA machine using the same software version, at each measurement**. DEXA scans should be scheduled to occur prior to CT or MRI tumor measurements. In the event that a CT scan with contrast is obtained prior to a DEXA scan (such as scans done for standard of care), then there must be a **10 day washout prior to obtaining the DEXA scan**. Subjects who discontinue study prior to C3D1 will not receive a second DEXA scan. An off study lean body mass/body composition DEXA scan should be performed at the End of Study Visit for any subject who completes visits at least through C3D1, but discontinues prior to the C5D1 DEXA.

^h The EORTC QLQ-C30 (version 3) is a validated quality of life instrument for cancer patients. It consists of 30 items that encompass 3 symptom scales (pain, fatigue, nausea/vomiting), 6 single-item symptom items, 5 functional scales (physical, cognitive, role, emotional, and social), and one scale assessing global health status/quality of life. Each scale consists of 2-5 items. All items have four response categories (not at all, a little, quite a bit, very much), except for 2 items assessing overall health status/quality of life, which use a seven-point scale.

ⁱ Assessments can include CT or MRI, and whichever modality is chosen for the initial tumor assessment must be used for the week 8 assessment (Cycle 5 Day 1). Tumor measurements should ideally be obtained after DEXA scans for body composition. If standard of care scans are used, then there should be a 10-day washout after any CT scan with contrast prior to obtaining the DEXA scan. The choice of modality should be based primarily on the type of scan that the patient has previously received as their standard of care. Standard of care scans obtained within 28 days of C1D1 can be used as screening scans. Tumor measurements are to be performed on Cycle 5 Day 1 +/- 3 days.

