7.1 Analysis Populations:

The primary efficacy analysis will be conducted on an intent-to-treat (ITT) basis. The ITT population will consist of all randomized patients. Patients will be grouped according to treatment group.

Some major changes were made to protocols version V3.0 onwards. Prior to V3.0 this trial was an open label, 1:1 random allocation study where patients received MABp1 (3.75 mg/kg) plus BSC or megestrol acetate plus BSC. Some of the major changes to protocols V3.0 onwards were a double blind placebo controlled design with 2:1 allocation ratio. Dosing regimen also changed from 3.75 mg/kg to 7.5 mg/kg of MABp1. Given the nature of change to the study design patients enrolled on protocols prior to V3.0 modification will not be included in the analysis.

A secondary analysis of the efficacy endpoints will be performed on Per Protocol (PP) patients. The PP population will be defined as those patients in the ITT set who are compliant with the study protocol. Patients will be grouped according to treatment groups.

The Safety analysis will be based on the Safety Population, defined as enrolled patients receiving at least one dose of study drug. Patients will be grouped according to actual treatment received.

7.2 Incomplete Follow-up:

Patients discontinued or lost prior to cycle 3 visit (and therefore not having the second DEXA), or those discontinuing between cycles 3 and 5 but did not complete off-study visit, will not be included for secondary efficacy outcome assessment for absolute change in LBM, or EORTC endpoints.

For the PFS assessment, patients discontinued or lost without evidence of tumor progression will be censored according to Table 1 .

7.3 Missing Data:

Every effort will be made to identify and recover the missing data from the centers. If the data remained missing following such efforts, and contributes 2% or more of total number of patients for the continuous co-variables selected for the Cox model, it will be imputed through multiple imputations (using SAS PROC MI, pooled by PROC MIANALYZE option). Sensitivity analysis will be performed to assess the effect of imputation.

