7.4 Outliers

No formal outlier tests are planned. Normally distributed values that are outside 3 standard deviations from the mean will be queried and verified with source prior to database lock. Tukey's 3-inter-quartile range (IQR) principle² for outlier detection will be utilized for identifying extreme values in platelet count and laboratory measures. Values outside 3 times of 5th and 95th quantile range will be considered as extreme values. If extreme values are present, a sensitivity analysis will be performed after removing the extreme values.

7.5 Derived and Computed Variables:

Patient's age (in years) at randomization is a derived field in the remote capture database, which is rounded to an integer value after subtracting date of birth from the randomization date and dividing the results by 365.25 days.

Change from Baseline

For the continuous variables or variables with linear transformation (e.g. EORTC score), the change at follow-up will be calculated by subtracting the value on screening visit from that on the follow-up visit (week 8 or end of study visit, as appropriate). Percent change will be computed as $(\text{post-value} - \text{pre-value})/\text{pre-value} * 100$.

8 Statistical Analyses

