8.4.1 Primary Efficacy Endpoint

Subjects who are alive at the data inclusion cutoff date for the analysis will be censored at that date and survival time will be defined as time from randomization to censor date. Patients lost to follow-up and untraceable for survival status will be censored on the last date subject was known to be alive or lost to follow-up. A censoring variable will be created identifying a censored observation. The primary endpoint, overall survival, will be summarized by Kaplan-Meier method and compared between the treatment groups using an un-adjusted log-rank test. The median survival, and cumulative survival probability along with 95% confidence interval (CI) calculate by log-log transformation and 25th and 75th percentiles will be reported according to randomization arms. Kaplan-Meier curves will be generated plotting the estimated survival density function over time. Number of patients at risk on various time intervals will be presented on the curve. The type I error rate to be used for determining statistical significance of the primary outcome is defined in section 5.1 “Interim Efficacy Analyses”.

The primary efficacy analysis will also be conducted for the PP population.

A secondary supportive analysis will be performed comparing survival probabilities across treatment groups, stratified separately by age (dichotomizing at median), gender, ECOG performance status, KRAS mutation status and prior treatment with regorafenib, and number of prior antineoplastic therapies. Survival probabilities and 95% CI for the 25th, median and 75th percentiles will be reported by treatment groups and stratum. No multiplicity adjustment will be made for this supportive analysis.

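### The exploratory comparison of overall survival by clinical response (SAP 8.4.3) runs from randomisation, so guaranteed survival time favours responders

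*SAP*

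**What the plan says.** - **The comparison.** SAP 8.4.3, which covers further exploratory work, states: "Additional analyses will be performed comparing the primary overall survival endpoint, the secondary endpoints, and incidence of SAE, between Clinical Responders and Non-responders". On method: "The statistical methodology in conducting these analyses will follow the same described in the primary and secondary efficacy analysis and safety analysis sections".
- **What it inherits.** SAP 3.1 sets the OS clock: "survival time will be defined as the duration from the date of randomization until death". SAP 8.4.1 gives the test: OS is "compared between the treatment groups using an un-adjusted log-rank test".
- **When response is known.** SAP 3.2 takes change from baseline at "follow-up (cycle 5 day 1 or off-study visit for patients who completed at least cycle 3 day 1"); SAP 7.5 words it as "week 8 or end of study visit, as appropriate". SAP 7.2 describes those without the measurement: "Patients discontinued or lost prior to cycle 3 visit (and therefore not having the second DEXA"). Footnote g of the protocol's Study Calendar agrees: "Subjects who discontinue study prior to C3D1 will not receive a second DEXA scan".
- **No follow-up.** SAP 3.3 and the Clinical Response Rate paragraph of SAP 8.4.2 class patients without a follow-up assessment as non-responders.
- **Population.** SAP 8.4 names ITT and PP. SAP 8.4.3 does not say whether arms are pooled, stratified or limited to Xilonix. For the Clinical Response Rate summary, SAP section 9 names the Xilonix arm only, while table shells 6 and 7 show both arms.

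Neither document gives a landmark, a time-dependent covariate or any other correction.

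**The concern.** Response is learned weeks after randomisation, but the OS clock starts at randomisation. Responders cannot die in that interval. Every death before C3D1 is a non-responder by definition, and so is a later death that comes before any follow-up assessment. This is guaranteed-time (immortal-time) bias.

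It matters because the protocol's rationale (sections 1.1 and 1.5) is that lean-mass gain goes with longer survival. As written, this analysis can appear to confirm that when no relation exists.

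Two smaller problems sit in the same paragraph. Lean body mass (LBM) and the three EORTC symptom scales define response, so testing them by response status is circular. PFS and SAEs are also compared by a status learned after randomisation, with unequal observation time.

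**Working it through.** **1. The plan's own figures.** The documents give no figure for this comparison. Their design hazards reproduce: ln2/4.6 = 0.1507 per month (stated 0.151) and ln2/6.0 = 0.1155 (stated 0.116). The 552 deaths also reproduce: simulating the three-stage design with the SAP's efficacy and futility cut-offs gives power 0.798 against the stated 80%.

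**2. Deaths before assessment.** Proportion dead by day t = 1 − exp(−hazard × t/30.44), with 200 control and 400 Xilonix patients.

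| Day from randomisation | Control | Xilonix | Deaths of 600 |
|---|---|---|---|
| 28 | 12.9% | 10.1% | 66 |
| 56 | 24.2% | 19.1% | 125 |
| 70 | 29.3% | 23.3% | 152 |

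C3D1 falls 28 days after C1D1, and C1D1 may be up to 7 days after randomisation, so day 28 is a lower bound for the guaranteed time. Deaths between C3D1 and C5D1 also fall among non-responders unless an off-study assessment came first.

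**3. A hand check.** Take the Xilonix arm (400), assessment at day 56 (1.84 months), no off-study capture, no censoring, and response given at random to 36% of survivors.

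- Deaths by day 56: 400 × 0.1915 = 76.6. Survivors: 323.4. Responders: 0.36 × 323.4 = 116.4. Non-responders: 400 − 116.4 = 283.6, of whom 207.0 were alive at day 56.
- Mean survival after day 56 is 1/0.1155 = 8.66 months for every survivor.
- Responder death rate: 1/(1.84 + 8.66) = 0.0953 per month.
- Non-responder person-months: before day 56, 76.6 × 8.66 − 116.4 × 1.84 ≈ 449; afterwards, 207.0 × 8.66 ≈ 1,792; total about 2,241. Death rate: 283.6/2,241 = 0.1266.
- Rate ratio from randomisation: 0.0953/0.1266 = 0.75. Counted from day 56, both rates are 0.1155 and the ratio is 1.00.

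Simulating this setting with censoring at 18 months gave a Cox hazard ratio (HR) of 0.72 and p<0.05 in 79% of trials.

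**4. Simulation, both arms, response unrelated to survival.** Assumed: 36% response among those assessed (the pilot colorectal lean-mass rate in protocol 1.5, used only as an anchor) and constant hazard at the planned medians.

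| Analysis | HR | p<0.05 |
|---|---|---|
| From randomisation, censoring 6–18 months | 0.65–0.78 | 68–99% |
| From randomisation, 18-month follow-up | 0.69–0.81 | 63–97% |
| Day-70 landmark | 0.99–1.01 | about 5% |

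The stronger bias goes with no off-study capture of deaths between C3D1 and C5D1, the weaker with full capture. Censoring at 6–18 months yields about 454 deaths. Following everyone for 18 months yields about 200 × 0.934 + 400 × 0.875 = 537, nearer the planned 552.

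**5. Lower early mortality.** Inclusion criterion 12 asks for patients judged fit to stay on the trial for three months. Hazard was lowered in the first three months and raised later to keep the medians, with response of 20, 36 or 50%, off-study capture of 0, 50 or 100% and 0 or 15% other missing data. Half the early hazard gives HR 0.76–0.92 (p<0.05 in 9–87%); a quarter gives 0.87–0.97 (5–35%).

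**6. Timing of a landmark.** The latest undelayed C5D1 scan is at 7 + 56 + 3 = day 66, or day 68 if the ±2-day visit window adds. An off-study visit may come up to 14 days after discontinuation (protocol 5.4), so up to about 7 + 56 + 14 = day 77, or day 91 with a 14-day treatment delay.

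**The case against.** The strongest reply is that the analysis is labelled exploratory and carries no alpha. That is true and limits the consequence. A reader might infer that the trial's main result is at risk. It is not: the primary test compares randomised arms, and the between-arm response rate properly counts missing patients as non-responders.

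The second reply is that the size is assumption-driven. This stands. The documents give no planned response rate, off-study capture, early hazard or censoring pattern, and the simulations do not model in detail patients who stop treatment but live on. No single HR should be read as what this trial would show. The direction does not depend on these inputs.

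Third, a reader might say that the population is unstated. That goes too far: SAP 8.4 names ITT and PP, and 8.4.3 sits under it. Only arm handling is open. The conflict between section 9 and shells 6 and 7 concerns the response-rate summary and needs separate reconciling.

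Fourth, no convenient landmark captures every permitted assessment. Day 70 misses some off-study visits, about 2% of them if discontinuation and visit timing are uniform (an assumption). Day 84 misses the latest delayed ones. This argues for a separate unassessed group, not against a landmark.

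**Conclusion.** The concern holds for OS. As written, the comparison favours responders by construction. Under 36% response, both arms and constant hazard, the spurious HR is about 0.65–0.81, with p<0.05 in about 63–99% of trials. The bias alone can thus match or exceed the design effect of 0.767. With much lower early mortality it shrinks to about 0.87–0.97.

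The documents do not support extending a quantified bias to PFS or SAEs. A patient can progress after C3D1, have the off-study scan and still be a responder, and SAP Table 3 censors some early discontinuations. SAEs are collected only to 30 days after the last dose, and the direction of that effect is unknown. For these endpoints the supportable statement is that observation time is unequal.

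This should be corrected before the analysis is run. It does not bear on the trial's primary conclusion.

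**What to change.** In SAP 8.4.3:

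1. Analyse OS by response from a landmark at a fixed day from randomisation, for example day 70. Include patients alive and in follow-up then, use only C5D1 or off-study data available by then, restart the clock, and show unassessed patients as a separate group. Use a later landmark, such as day 84, as a sensitivity analysis.
2. State arm handling: Xilonix only, or both arms stratified by arm. Reconcile section 9 with shells 6 and 7.
3. Do not test LBM or EORTC symptom change by response status.
4. For PFS and SAEs, apply the same landmark principle or report descriptively, stating the unequal observation time.
5. State that a landmark does not remove prognostic confounding (protocol 1.1 itself calls lean-mass loss prognostic), so the result is an association.

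Also reconcile the EORTC questionnaire at the End of Study visit: the protocol 5.4 procedures list it, but the Study Calendar does not mark it there, and response needs both scan and questionnaire. Keep missing-as-non-responder for the between-arm response rate.

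The cost is wording. Early deaths leave this one analysis: at day 70 about 600 − 152 = 448 patients remain under constant hazard, and up to about 558 if early mortality is a quarter of that. Precision falls, and the result will look less favourable.
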